Appendix 4 Drugs Known to Interact with CYP3A4

SUBSTRATES: 3A4,5,7

Macrolide antibiotics:

clarithromycin
erythromycin (not 3A5)
NOT azithromycin
telithromycin

Anti-arrhythmics:

quinidine-OH (not3A5)

Benzodiazepines:

alprazolam
diazepam-3OH
midazolam
triazolam

Immune Modulators:

cyclosporine
tacrolimus (FK506)

HIV Antivirals:

indinavir
nelfinavir
ritonavir
saquinavir

Prokinetic:

cisapride

Antihistamines:

astemizole
chlorpheniramine
terfenadine

Calcium Channel Blockers:

amlodipine
diltiazem
felodipine
lercanidipine
nifedipine2
nisoldipine
nitrendipine
verapamil

HMG CoA Reductase

Inhibitors:

atorvastatin
cerivastatin
lovastatin
NOT pravastatin
NOT rosuvastatin
simvastatin

Steroid 6beta-OH:

estradiol
hydrocortisone
progesterone
testosterone

Miscellaneous:

alfentanyl
aprepitant
aripiprazole

buspirone
cafergot
caffeine_TMU
cilostazol
cocaine
codeine-
Ndemethylation
dapsone
dexamethasone
dextromethorphan
docetaxel
domperidone
eplerenone
fentanyl
finasteride
gleevec
haloperidol
irinotecan
LAAM
lidocaine
methadone
nateglinide
ondansetron
pimozide
propranolol
quetiapine
quinine
risperidone
salmeterol
sildenafil
sirolimus
tamoxifen
taxol
terfenadine
trazodone
vincristine
zaleplon
ziprasidone
zolpidem

INHIBITORS 3A4,5,7

HIV Antivirals:

indinavir
nelfinavir
ritonavir

Antibiotics

clarithromycin
itraconazole
ketoconazole
nefazodone
saquinavir
telithromycin
aprepitant
erythromycin
fluconazole

Grapefruit juice

Miscellaneous

verapamil
diltiazem
cimetidine
amiodarone
NOT azithromycin
chloramphenicol
ciprofloxacin
delaviridine
diethyldithiocarbamate
flvoxamine
gestodene
imatinib
mibefradil
mifepristone
norfloxacin
norfluoxetine
star fruit
voriconazole

INDUCERS 3A4,5,7

HIV Antivirals:

efavirenz
nevirapine

Miscellaneous

barbiturates
carbamazepine
glucocorticoids
modafinil
oxcarbazepine
phenobarbital

phenytoin
pioglitazone
rifabutin
rifampin
St. John's wort
troglitazone

© Cytochrome P450 Drug Interaction Table
www.drug-interactions.com

Appendix 5 Drugs that may Interact with P-glycoprotein

Transporter	MDR1/PgP
Gene	ABCB1
Amiodarone	S/Inhib
Amitriptyline	Inhib
Amprenavir	Induc
Astemizole	Inhib
Atorvastatin	S/Inhib
Boceprevir	S/Inhib
Bromocriptine	Inhib
Carvedilol	Inhib
Chlorpromazine	Inhib
Clarithromycin	Inhib
Clotrimazole	Induc
Cyclosporine	S/Inhib
Desipramine	Inhib
Dexverapamil	Inhib
Diltiazem	S/Inhib
Dipyridamole	Inhib
Disulfiram	Inhib
Doxepin	Inhib
Erythromycin	S/Inhib
Fluphenazine	Inhib
Glibenclamide	Inhib
Haloperidol	Inhib
Imipramine	Inhib
Indinavir	S/Induc
Itraconazole	S/Inhib
Ketoconazole	Inhib
Lidocaine	S/Inhib
Lovastatin	S/Inhib
Maprotiline	Inhib
Mefloquine	Inhib
Meperidine	Inhib
Methadone	Inhib
Mibefradil	Inhib
Midazolam	Inhib
Mifepristone	Inhib
Nelfinavir	S/Induc
Nicardipine	S/Inhib
Nifedipine	Inhib

Ofloxacin	Inhib
Pentazocine	Inhib
Prazosin	Induc
Prochlorperazine	Inhib
Progesterone	Inhib/Induc
Propafenone	Inhib
Propranolol	S/Inhib
Quercetin	Induc
Quinidine	S/Inhib
Quinine	Inhib
Reserpine	inhib
Retinoic acid	Induc
Rifampin	S/Induc
Ritonavir	S/inhib
Saquinavir	S/Inhib
Simvastatin	S/Inhib
St. Johns Wort	Induc
Tacrolimus	S/Inhib
Tamoxifen	Inhib
Telaprevir	S/Inhib
Temsirolimus	S/Inhib
Testosterone	Inhib
Trimipramine	Inhib
Vasopodar	Inhib
Verapamil	S/Inhib

Inhib = Inhibition;

Induc = Induction;

S = Substrate;

MDR = multidrug resistance protein

Source: Pharmacology Weekly

<http://www.pharmacologyweekly.com/content/pages/medications-drugs-substrates-inhibitors-inducers-efflux-transporters>

## 1 SUMMARY OF CHANGES

SAP Version History		
Version	Date	Description of Changes
1.0	June 19, 2017	Original Document
2.0	September 6, 2017	Modify TEAE to include all AEs starting on or after dosing by removing “or exist before but get worse in severity or relationship to study drug after first dose.”  Also urinalysis is only collected at Screening and Final Study Visit. Remove summaries by dose level for Day 1 and Day 15.

## 2 INTRODUCTION

This Statistical Analysis Plan (SAP) provides a description of the statistical and pharmacokinetic (PK) methods and procedures to be implemented for the analyses of data from Millendo Therapeutics Protocol ATR-101-201. Any deviations from this analysis plan will be substantiated by sound statistical/PK rationale and will be documented in the final clinical study report.

## 3 STUDY OBJECTIVES

### 3.1 Primary Objective

The primary objective of this study is to evaluate the efficacy and safety of orally administered ATR-101 in subjects with congenital adrenal hyperplasia (CAH).

### 3.2 Secondary Objectives

The secondary objectives of this study are:

- To evaluate the changes in adrenal cortical steroids and steroid intermediates
- To evaluate the changes to the hypothalamic-pituitary-adrenal axis (via adrenocorticotrophic hormone [ACTH])
- To evaluate the PK of ATR-101

## 4 STUDY ENDPOINTS

#### 4.1 Efficacy Assessment

Efficacy will be assessed by changes in adrenal steroids and steroid intermediates.

17-hydroxyprogesterone (17-OHP) will serve as the **primary outcome measure** as this adrenal steroid intermediate is used diagnostically and to aid in the management of exogenous glucocorticoid (GC) replacement therapy in clinical practice. However, absolute target values for 17-OHP or androgens do not currently exist in treatment guidelines put forth by any of the medical societies. The entry criterion for 17-OHP is set at  $\geq 4x$  upper limit of normal (ULN) (ULN adjusted as needed for the menstrual cycle phase of subjects who are premenopausal women), which is intended to enroll subjects who are not optimally controlled while on exogenous steroid replacement therapy. It is anticipated that most subjects will enter with 17-OHP levels markedly higher than  $4xULN$ . The primary efficacy outcome measure will be aligned to the clinical goal of achieving a mildly elevated 17-OHP level, which for this study is defined as  $\leq 2xULN$ . However, given the high baseline 17-OHP levels anticipated, the percentage change in 17-OHP and changes in other key efficacy parameters in the androgen pathway (androstenedione, testosterone, dehydroepiandrosterone [DHEA], dehydroepiandrosterone sulfate [DHEA-S]) will also serve to define efficacy.

The majority of CAH subjects will enter the study on both GC and mineralocorticoid (MC) replacement (75% of classic CAH subjects have deficiencies in both pathways). Direct renin and aldosterone will be assessed to determine the potential impact on the MC pathway.

ACTH levels will be assessed to determine potential effects on the hypothalamic-pituitary-adrenal (HPA)-axis. GC replacement doses are expected to remain unchanged. Confirmation of low GC levels associated with decreases in 17-OHP and androgens with ATR-101 dosing will help to establish the pharmacodynamic effects of ATR-101. Increased GC levels, secondary to decreased hepatic metabolism (ATR-101 CYP3A effect), could potentially lead to decreased ACTH and subsequently decreased 17-OHP levels. This could potentially confound assessment of direct ATR-101 effects on adrenal steroid and steroid intermediate synthesis. Therefore, assessment of GC levels will also be done during the study.

#### 4.2 Safety Assessment

[figure not shown]
Safety will be assessed by monitoring adverse events (AEs), changes in physical examination (including vital signs), changes in electrocardiograms (ECGs), and changes in laboratory parameters. Safety assessments will take place every 2 weeks during study participation.

## 5 STUDY OVERVIEW

### 5.1 Study Design

This is a multicenter, single-blind, multiple dose study of ATR-101 with a placebo washout component. A minimum of nine subjects will be enrolled with the potential to add an additional eight subjects. The study design is presented in Figure 1 below.

**Figure 1. ATR-101-201 Study Design**

Each subject will complete a Screening Period of up to 21 days to assess inclusion and exclusion criteria. Baseline status will be established with a 14-day single-blind, placebo Lead-in Period. Exogenous GC and MC replacement therapy must be maintained throughout the duration of the study. Each dose level, comprised of ATR-101 administered for 14 days followed by a 14-day placebo washout, will last for a total of 28 days (see Figure 2 below). All subjects will start at Dose Level 1, ATR-101 125 mg twice daily (BID), for 14 days. Efficacy and safety will be assessed after the 14-day ATR-101 treatment period (on the morning of Day 15). Immediately after the completion of the ATR-101 treatment period, a 14-day single-blind, placebo Washout Period (placebo matching ATR-101 125 mg) will take place. The efficacy assessment obtained on Day 15 will be reviewed by the Principal Investigator (PI) or Sub-investigator (SI) to determine whether the subject has met the

primary outcome measure or whether the subject should continue to the next dose level (if there are no safety issues).

**Figure 2. Dosing Regimen per Dose Level**

ATR-101 BID	Day 1	Day 2	Day 3	Day 4	Day 5	Day 6	Day 7
	Day 8	Day 9	Day 10	Day 11	Day 12	Day 13	Day 14
Placebo BID	Day 15	Day 16	Day 17	Day 18	Day 19	Day 20	Day 21
	Day 22	Day 23	Day 24	Day 25	Day 26	Day 27	Day 28

Subjects will return to the study center after completion of the 14-day placebo Washout Period and will follow one of two actions based upon **Day 15** efficacy results:

- If the primary outcome measure is met (i.e., **17-OHP** ≤ **2xULN**) the subject completes the Final Study Visit
- If the primary outcome measure is **not** met (i.e., **17-OHP** > **2xULN**) the subject continues to the next dose level.

Table 1 below presents the 5 ATR-101 Dose Levels. Dose Levels 2, 3, 4, and 5 will follow the same procedures as Dose Level 1 (i.e., treatment with ATR-101 for 14 days, followed by the placebo Washout Period of 14 days). A subject may receive a minimum of one dose level (Level 1) or a maximum of 5 dose levels (Level 1-5), along with the corresponding placebo Washout Periods.

**Table 1. ATR-101 Doses for Each Dose Level**

Dose Level	ATR-101 Dose	Total Daily Dose
1	125 mg BID	250 mg
2	250 mg BID	500 mg
3	500 mg BID	1000 mg
4	750 mg BID	1500 mg
5	1000 mg BID	2000 mg

## 5.2 Treatments Administered and Blinding

During the 14-day Baseline Lead-in Period, placebo tablets that match the ATR-101 125 mg tablets will be administered BID.

Starting with Dose Level 1, each dose level will consist of a 28-day dosing regimen consisting of 14 days of ATR-101 treatment followed immediately by 14 days of matching placebo washout.

Subjects will be blinded to treatment beginning with the Baseline Lead-in Period, which will use placebo tablets that appear identical to ATR-101 125 mg. Dose levels 1 to 5 are split into two weeks of active treatment (ATR-101) followed by two weeks of treatment with matching placebo (Washout Period).

## **6 STATISTICAL METHODOLOGY**

### **6.1 Sample Size Determination**

Sample size considerations are based on a Simon 2-stage Minimax design with 1-sided alpha of 5% and 80% power.

Stage 1 consists of 9 completed subjects. The study will stop at Stage 1 if either of the following conditions are met:

- Futility criteria: defined as  $\leq 2$  of 9 (22%) subjects having a Day 15 17-OHP  $\leq 2 \times \text{ULN}$  or a negative mean percentage change (i.e., decrease) in 17-OHP from Day 1 to Day 15 for Dose Levels 1-5
- Success criteria: defined as  $\geq 7$  of 9 (78%) subjects having a Day 15 17-OHP  $\leq 2 \times \text{ULN}$  or a negative mean percentage change (i.e., decrease) in 17-OHP from Day 1 to Day 15 for Dose Levels 1-5

Stage 2 will commence if 3, 4, 5, or 6 of the 9 subjects meet the primary outcome measure. In this scenario, accrual will continue with up to 8 additional subjects for a total of no more than 17 subjects. Accrual may stop earlier with sufficient evidence for further development if a total of 7 or more subjects respond (minimum observed response rate of 7/17, 41%).

The study medical monitor along with the Sponsor may determine if a subject will be replaced in order to have a minimum of 9 evaluable subjects for Stage 1. Possible reasons for replacement include extreme noncompliance with study drug not related to an AE, and noncompliance with the protocol such as the use of prohibited medications that could confound results.

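### SAP 6.1 moves the Stage 1 stopping rules to a composite endpoint but leaves the Stage 2 trigger and the Simon bounds on the old one, so the go/no-go rule contradicts itself or carries error rates not derived for it

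*SAP*

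**What the plan says.** Protocol 9.1 uses one endpoint, 17-OHP ≤2×ULN, for all parts of the rule: stop for futility at ≤2 of 9, stop for success at ≥7 of 9, otherwise go to Stage 2, with 7 of 17 as the final bound.

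SAP 6.1 changes the endpoint for futility and success only. A subject now counts with Day 15 17-OHP ≤2×ULN "or a negative mean percentage change (i.e., decrease) in 17-OHP from Day 1 to Day 15 for Dose Levels 1-5". The rest of the section stays as it was:

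- The design statement: "Sample size considerations are based on a Simon 2-stage Minimax design with 1-sided alpha of 5% and 80% power".
- The trigger: "Stage 2 will commence if 3, 4, 5, or 6 of the 9 subjects meet the primary outcome measure".
- The final bound: "Accrual may stop earlier with sufficient evidence for further development if a total of 7 or more subjects respond".

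The SAP says elsewhere what these terms mean. Section 4.1 describes the primary efficacy outcome measure as "aligned to the clinical goal of achieving a mildly elevated 17-OHP level, which for this study is defined as" ≤2×ULN. Section 5.1 (text under Figure 2) applies the same threshold subject by subject: "If the primary outcome measure is met" the subject has the final visit, and if not, "the subject continues to the next dose level". Section 6.8 defines a responder as meeting the primary outcome measure on Day 15 at any dose level, and gives the composite a separate name, 'drug effect'.

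SAP 7 discloses the change to futility and success and attributes it to medical considerations. It does not mention the Stage 2 trigger, the 7/17 bound, or new error rates.

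**The concern.** Two of the four parts of the decision rule moved to a new endpoint and two did not. The new endpoint is also much easier to meet by chance, because any mean decrease counts, however small. There are two possible readings, each with its own defect:

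- **Literal reading** (the trigger and 7/17 stay on ≤2×ULN). Stage 1 is judged on two counts at once, so the criteria need not agree or cover every result.
- **Composite throughout.** Every result has one action, but the bounds and the 5%/80% statement belong to a different endpoint. SAP 6.8 tabulates a parallel 'placebo effect' composite, so the SAP recognises that the criterion can be met off drug. The decision rule takes no account of that rate.

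At stake is the choice between stopping at 9 subjects and continuing to 17, and the error rates claimed for that choice.

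**Working it through.** **1. Reproduce the stated design.** Neither document gives p0 or p1. An exhaustive Minimax search (alpha ≤5%, power ≥80%) with p0 = 20% and p1 = 50% returns exactly the SAP's bounds, r1/n1 = 2/9 and r/n = 6/17. This pair is inferred. With X1 ~ Bin(9, p) and X2 ~ Bin(8, p),

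P(success) = Σ over x = 3 to 6 of P(X1 = x)·P(X2 ≥ 7 − x) + P(X1 ≥ 7).

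At p = 0.20: 0.1762×0.0563 + 0.0661×0.2031 + 0.0165×0.4967 + 0.0028×0.8322 + 0.0003 = 0.034. At p = 0.50 the same formula gives 0.806. The probability of stopping for futility at p = 0.20 is 0.738. So 5%/80% is met for a single endpoint with these rates.

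**2. Literal reading: enumerate Stage 1.** Let R be the number of subjects at ≤2×ULN and C the number meeting the composite. Then R ≤ C ≤ 9, which gives 55 pairs.

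| C | R | Stated action | Pairs |
|---|---|---|---|
| 0–2 | any | futility | 1+2+3 = 6 |
| 3–6 | 3–6 | Stage 2 | 1+2+3+4 = 10 |
| 3–6 | 0–2 | **none** | 4×3 = 12 |
| 7–9 | 0–2 or ≥7 | success | 4+5+6 = 15 |
| 7–9 | 3–6 | **success and Stage 2** | 3×4 = 12 |

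For example, C = 8 with R = 4 has two actions, and C = 5 with R = 1 has none. This step needs no assumptions, but it counts outcomes and is not a probability.

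**3. Composite throughout: the bounds at other null rates.** Put p equal to the chance that a subject with no drug effect meets the composite. The formula in step 1 reaches 0.05 at p = 0.216. Beyond that:

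| p | 0.25 | 0.30 | 0.40 | 0.50 |
|---|---|---|---|---|
| P(success) | 0.098 | 0.208 | 0.521 | 0.806 |

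**4. How large might p be?** The documents give no within-subject CV, so a range is shown. Assumptions: no drug effect, independent lognormal values at each visit, and an arithmetic mean of five percentage changes. Five levels are used because a subject who completes without responding goes on to Level 5.

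| CV | 10% | 20% | 30% | 50% | 80% | 100% |
|---|---|---|---|---|---|---|
| P(negative mean % change) | 0.450 | 0.404 | 0.363 | 0.300 | 0.240 | 0.216 |
| False success, composite throughout | 0.68 | 0.53 | 0.40 | 0.21 | 0.08 | 0.05 |

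The rate falls with CV because percentage changes are right-skewed. Averaging fewer levels raises it: 0.50 at any CV for one level, and 0.469 down to 0.309 for three.

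**5. How often does the literal rule fail?** Same no-effect model, with an assumed typical 17-OHP level. SAP 4.1 supports high levels: "It is anticipated that most subjects will enter with 17-OHP levels markedly higher than" 4×ULN.

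| CV | 10% | 20% | 30% | 50% | 80% | 100% |
|---|---|---|---|---|---|---|
| P(no stated action), 8×ULN | 0.80 | 0.75 | 0.68 | 0.54 | 0.49 | 0.38 |
| P(no stated action), 16×ULN | 0.80 | 0.75 | 0.68 | 0.53 | 0.39 | 0.36 |

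False success under this reading is 5.4–6.1% at 8×ULN with CV 100%, depending on how two-action results are scored, and at most 5% in the other cells. Double actions arise mainly when the drug works. With 50% responders and an assumed composite rate of 60/70/80/90%, their probability is 14/37/61/78%.

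**The case against.** - **The intended reading may be the composite throughout.** A trigger of 3 to 6 is the exact complement of ≤2 and ≥7, which suggests a single count, and SAP 4.1 adds that percentage change in 17-OHP also helps define efficacy. This stands as a reason to keep the readings apart. The two harms never occur together: gaps and overlaps belong to the literal reading, and inflated alpha to the composite one. But SAP 5.1 and 6.8 define the unchanged terms as ≤2×ULN, so the literal reading rests on the SAP's own vocabulary.
- **A mixed reading is milder.** If the composite governs Stage 1 while the 7/17 rule keeps the responder definition, every Stage 1 count has one action. The chance of ≥7/9 with no effect is then 0.050/0.027/0.014/0.004/0.001/0.0005 at the six CVs. That makes 68% one end of a range. The reading takes two linked terms in different senses, though, and still leaves 5%/80% underived.
- **Precedence could settle it.** Letting the stopping rule win would resolve the two-action results. The SAP does not say so, and precedence does nothing for the 12 results with no action.
- **The stakes are limited.** Analyses are descriptive, the endpoint change is disclosed with a reason, and the reported responder rate is untouched. All true. Even so, the SAP claims an alpha and a power, and this rule sets the sample size.
- **The probabilities use assumed inputs.** Correct. Only the 12/12 count and the 21.6% threshold are free of assumptions about 17-OHP variability, levels or response rates.

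**Conclusion.** The concern holds and should be fixed before the rule is used. The edit to SAP 6.1 is incomplete. Taken with the SAP's own definitions, 24 of 55 possible Stage 1 results have either two actions or none. Under the assumed no-effect model, a result with no action has probability between 36% and 80%. The defect of this reading is the missing or double action; its false-success rate stays near or below 5%.

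Taken as the composite throughout, the rule can be carried out, but its 5% alpha fails once the no-effect composite rate passes 21.6%. With five independent lognormal levels that happens for any within-subject CV below about 100%.

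The harm is confined to the decision rule and its stated error rates. The inferred 20%/50% pair needs the sponsor's confirmation.

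**What to change.** In SAP 6.1 and 7, use one endpoint for Stage 1 futility, Stage 1 success, the Stage 2 trigger and the 7/17 rule.

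1. **Day 15 17-OHP ≤2×ULN throughout.** State p0 and p1 (20%/50% reproduces the bounds), keep the 5%/80% statement, and leave 'drug effect' in SAP 6.8 as descriptive. Cost: wording only. A go decision may become harder to reach, and a decrease that stays above 2×ULN would inform it only descriptively.
2. **The composite throughout**, with a pre-specified minimum decrease. Replace the 5%/80% statement with recomputed bounds and error rates. Cost: a new calculation and possibly a different size. For illustration, with an assumed null rate of 50%, Minimax gives 10/15 and 11/17 for a target of 80%, and 7/14 and 15/23 for a target of 75%.

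In either case, state in SAP 7 whether the change was made before Stage 1 results were seen. Protocol 9.9 says efficacy results are not blinded to the sponsor, and SAP version 1.0 (June 19, 2017) comes 17 months after Protocol Amendment 1 (January 14, 2016). The documents do not show that results were seen first, so this is a question for the sponsor to answer.

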### **6.2 General Considerations**

Unless otherwise specified, summaries will be presented by dose level where the first dose of ATR-101 defines the start of each dose level. In other words, each dose level consists of Day 1 – Day 28 (2 weeks of ATR-101 and 2 weeks of Placebo). Subjects may be counted in more than one dose level. Each subject will be counted once in each dose level according to sequential participation and once in the overall column.

In addition, summaries will be provided by last dose level. In other words, the results from the subject's last completed dose level will be carried forward.

## **6.3 Analysis Populations**

### **6.3.1 Enrolled Population**

The Enrolled Population will include all subjects who receive at least one dose of placebo during the Lead-in Period.

### **6.3.2 Safety Population**

The Safety Population will include all subjects who receive at least one dose of ATR-101. For summaries by dose level, only subjects receiving at least one dose in the specified dose level will be included. For summaries by dose level and treatment, only subjects receiving at least one dose in the specified dose level treatment will be included.

### **6.3.3 Per Protocol Population**

The Per Protocol Population will include all subjects who take at least 11 days of ATR-101 treatment at Dose Level 1 (the lowest dose level) and have at least one post-baseline efficacy assessment (i.e. 17-OHP) without having a significant protocol deviation. The Per Protocol Population will be identified per dose level. All subjects excluded from the Per Protocol Population will be identified after database lock.

### **6.3.4 Pharmacokinetic Population**

The PK Population will include all subjects who receive at least one dose of ATR-101 and have any measurable level of ATR-101 or its metabolites.

## **6.4 Subject Disposition**

Counts of subjects in each population, as well as counts and percentages of subjects who completed the study and who withdraw early from the study, with the reason for early withdrawal, will be presented by ATR-101 dose level and overall.

## **6.5 Demographic and Baseline Characteristics**

Descriptive summaries of demographic and baseline characteristics will be presented by dose level and overall. Baseline measurements refer to data collected at Dose Level 1 Day 1 pre-dose. If a value at Dose Level 1 Day 1 pre-dose is not available, the last measurement prior to the first dose of study drug will be used as the baseline value.

Demographic and baseline characteristics include, but are not limited to: age at informed consent, sex, race, ethnicity, baseline glucocorticoids, baseline glucocorticoid dose, baseline mineralocorticoid dose, body weight, height, body mass index (BMI), body surface area, steroid hormones, and steroid intermediates. Continuous variables (age, glucocorticoid dose, mineralocorticoid dose, body weight, BMI, steroid hormones, and steroid intermediates) will be summarized by subject count, mean, standard deviation, median, minimum, and

maximum. Categorical variables (race, sex, ethnicity, and glucocorticoids) will be summarized by the number and percentage of subjects in the corresponding categories.

Body surface area will be calculated as:

$$\sqrt{\frac{\text{Weight in kg} \times \text{Height in cm}}{3600}}$$

Demographics and baseline characteristics will be summarized based on the Safety Population. If the Per Protocol Population and the PK Population differ from the Safety Population, the demographics and baseline characteristics will also be summarized based on these populations. Demographics and baseline characteristics will also be summarized for male and female subgroups and for men and postmenopausal women (excludes females <50 years in age).

All medical history will be listed.

